Official Title:	Hypnosis for Chronic Pain Relief in Cancer Survivors
NCT number:	03867760
Document Type:	Study Protocol and Statistical Analysis Plan
Date of the Document:	January 28, 2019

RESEARCH PROTOCOL

Methods and Design

Design. The study design is a two-arm RCT. The study uses an expanded protocol from the pilot RCT. The primary outcome (pain intensity) and secondary outcomes (pain interference, anxiety, depression, fatigue, and sleep disturbance) will be assessed at baseline, mid-study, and end of study. In addition, pain intensity and anxiety will be assessed daily. Participants will be randomly assigned to the RHI or an attention control condition (relaxation recording). Furthermore, an extreme phenotype approach will be taken to study brain states as a mechanism for hypnosis-induced pain reduction. Five participants from each group who score low (score = 0 - 1)¹ on the hypnotic suggestibility scale and 5 participants from each group who score high (score = 4 - 5)¹ will be invited to undergo qEEG measurement.

Sample and Settings. A convenience sample of 100 cancer survivors with chronic pain will be recruited from the Seattle Cancer Care Alliance (SCCA) Survivorship Clinic. SCCA is a National Cancer Institute-designated comprehensive cancer center where more than 6,000 patients with cancer received treatment last year. In 2016, 194 patients were seen at the Survivorship Clinic (based on chronic pain prevalence estimate of 39%, 76 patients with pain).

Power Analysis. Table 1 shows the minimal detectable change in the mean of the RHI group that can be detected given a total sample of 100 participants and 80% power, based on standard deviations observed in our prior research.

Participant Inclusion and Exclusion Criteria. Participant inclusion criteria are: (1) self-reporting moderate or higher pain on average during the last week (> 3 on a 0-10 pain intensity numeric scale), (2) self-reporting chronic pain related to cancer or its treatment, (3) completed active cancer treatment other than maintenance therapy, (4) being \geq 18 years of age, (5) functional fluency in English, and (6) mentally and physically able to participate and complete surveys. Participant exclusion criteria are: (1) a history of seizure disorder and (2) a significant brain injury or skull defect. Both exclusion criterion may impact qEEG measurement. We will not exclude potential participants based on use of pain medication, rather we will collect this information (drug, dose) and control for it in the data analysis.

Participant Recruitment. Staff at the SCCA Survivorship Clinic will screen Survivor Surveys completed by patients prior to their initial clinic visit from the past 2 years and during the study to identify patients who meet the pain intensity inclusion criteria. Names and contact information for patients will be given to the research team who will mail an information letter describing the study. The letter will include an opt-out postcard to be returned if the patient is not interested in being contacted by telephone about the study. Two weeks after the letters are mailed, patients will be contacted by telephone to further screen for eligibility and describe the study. If the patient is eligible and interested in participating, verbal and written consent to participate will be obtained. A study visit will be scheduled at the UW Health Sciences Center (HSC) for completion of the Stanford Hypnotic Clinical Scale and assignment of the intervention. The consent form and baseline questionnaires will be mailed to the participant to sign and complete respectively and return at the Week 0 (baseline) study visit.

Group Assignment. A SPSS randomization program will yield group assignments which will be placed in opaque, sequentially numbered sealed envelopes. Once the participant returns the completed baseline questionnaires and completes the in-person hypnotic clinical measure at the Week 0 study visit, the appropriate envelope will be opened and the participant will be notified of his/her group assignment. Based on their high or low hypnotic suggestibility score, eligible participants will be invited to participate in the qEEG study arm.

Intervention/Independent Variables. *Hypnosis Intervention.* The RHI consists of four 12- 18-minute digital recordings that I will make using standardized hypnosis scripts for pain reduction² and upload to a MP3 player. The scripts were developed for patients with chronic pain and tested by a psychologist who is an expert in hypnosis research ([name], co-mentor). Participants will listen to the recordings daily for 28 days in the prescribed order (4 recordings for 3 days each, and then any recording for the remaining 16 days). Selected recordings will be noted by the participant on the Daily Diary. The script includes an induction, suggestions for how to access inner resources and manage pain, and post-hypnotic suggestions for permanence of hypnosis

Table 1. Minimal Detectable Change in RHI Group

For N=100 (50/group), 80% power, alpha = 0.05, two-sided

Pain Score Standard Deviation		
Small SD (1.0)	Expected SD (1.5)	Large SD (2.0)
-0.57	-0.85	-1.13

benefits and self-hypnosis practice. Attention Control. The relaxation recordings will be uploaded to a MP3 player. Four different 12- 18-minute recordings of the selected genre will be listened to daily for 28 days (same prescribed order as the RHI).

Table 2a. Instruments.

Aim	Study Measures	Variable Measured	Week 0	Daily	Week 2	Week 4
1	*PROMIS 29 v. 1.0 29-item questionnaire, Cronbach's α 0.92-0.97. ³	Pain interference, anxiety, depression, fatigue, sleep	X		X	X
1	*PROMIS v.1.0-Pain Intensity 3a 3-item questionnaire, Cronbach's α 0.92-0.97. ³	Pain intensity	X		X	X
2	*PROMIS Self-Efficacy for Managing Symptoms	Self-Efficacy	X			X
3	qEEG	Brain activity/state	X		X	X

* National Institute of Nursing Research (NINR) Common Data Elements

Table 2b. Instruments.

Aim	Study Measures	Variable Measured	Week 0	Daily	Week 2	Week 4
1	Daily Diary 9-item questionnaire completed at bedtime, feasibility of participants completing it on a daily basis was established in pilot study.	Pain intensity, anxiety, and use of RHI or relaxation recording (including which recording used)		X		
2	Stanford Hypnotic Clinical Scale for Adults 5-item scale, 20 minutes to administer, product-moment correlation between total score and Stanford Hypnotic Scale C total score 0.72. ¹	Hypnotic suggestibility	X			
2	Tellegen Absorption Scale 34-item multi-dimensional scale, ⁴ test-retest reliability 0.85. ⁵	Absorption (Imaginative involvement, tendency to become mentally absorbed)	X			
2	Credibility/Expectancy Questionnaire 4-item questionnaire, test-retest 0.62-0.78, Cronbach's α 0.84-0.85. ⁶	Treatment outcome expectancy	X			
1	Demographic Questionnaire 15-item questionnaire.	Socio-demographics; cancer & treatment, and pain history; comorbidities; pain interventions	X			
3	Structured Interviews Each interview is anticipated to last 20 minutes and will be audio-recorded.	Barriers and facilitators associated with undergoing qEEG measurement; how intervention works				X

Data Collection Schedule and Procedures. Study Enrollment. The research assistant (RA) will contact potential study participants by telephone to screen, obtain verbal consent, and schedule the Week 0 study visit at the UW HSC. Baseline questionnaires and consent form will be mailed to the participant with instructions to complete 1-2 days before the Week 0 study visit.

Week 0 Study Visit. The RA will meet with the participant to (1) collect completed questionnaires and signed consent form; (2) administer the Stanford Hypnotic Clinical Scale; (3) share group assignment; (4) provide teaching about the RHI or relaxation recording, and participant study responsibilities; (5) administer the Credibility/Expectancy Questionnaire; and (6) inform participant if they are eligible for the qEEG measurement. Participants who are ineligible for the qEEG measurement (or eligible but not interested in participating) will begin using the assigned intervention at home on the same day as the Week 0 visit. The RA will schedule telephone calls with ALL participants to complete study measures at Week 2 (within 5 days of using the assigned intervention for 14 days), and Week 4 (within 5 days of using the assigned intervention for 28 days). Structured interviews with the RA also will be conducted by telephone. Participants will be reminded to return the Daily Diary in the provided pre-posted return envelope. Participants in the qEEG study arm will undergo the first qEEG at the Week 0 visit and begin using the assigned intervention at this time. All qEEG measurements

will take place at the UW Integrative Brain Imaging Center (IBIC). Week 2 and Week 4 qEEGs will be scheduled at the Week 0 visit and will take place within one day of completing study measures.

qEEG Protocol: The participant will complete a 0-10 pain intensity numeric scale pre- and post-qEEG. During the qEEG, the intervention group participant will listen to the RHI and the attention control group participant will listen to the relaxation recording via the MP3 player (Table 3). The EEG technologist will fit an electrode cap with premeasured sites using the international 10/20 system⁷ to the participant's head and the participant's scalp and will prep the earlobes with Nuprep (Weaver and Company, Aurora, CO, USA). The electrode sites will be filled with Electro-Gel (Electro-Cap International, Eaton, OH, USA) and prepped to ensure impedance values between 3 and 5 Kohms between each electrode site and each ear individually. The signals will be amplified using a bandpass of 0.53-70 Hz and sampled at the rate of 250 Hz. for 10 minutes (eyes closed) with an EGI Geodesic EEG System 300 using 128-channel HydroCel Nets. Participants will be monitored throughout the recording to ensure that they remain awake.

Per the UW IBC, raw recordings will be band-pass filtered between 0.5-100 Hz, and exported to Matlab (MathWorks, Natick, MA, USA) and then remontaged to the average reference montage. Plotted data will be inspected for potential artifacts (e.g., evidence of eye blinks, eye movements, body movements) and entire epochs will be removed if one or more channels exhibit presence of artifact. qEEG spectrum will be calculated from the first 2 minutes of artifact-free data with fast Fourier transform using 4-second epochs with 1/32 seconds of overlapping window advancement factor. The relative EEG power will be computed for each of five bandwidths (delta, 1.5-4 Hz; theta, 4-8 Hz; alpha, 8-13 Hz; beta, 13-30 Hz; gamma, 30-55 Hz), and the power estimates will be used for all subsequent analyses by our research team. Relative power measures show a closer correspondence to underlying cortical activity than does absolute power.⁸

All participants will receive \$50 for their participation, which will be distributed as follows: after return of the baseline

Table 3. qEEG Measurement Timeline

	Pre-Session	During Session	Post-Session
Week 0	10 minutes eyes closed	13 minutes RHI or relaxation	10 minutes eyes closed
Week 2	10 minutes eyes closed	13 minutes RHI or relaxation	10 minutes eyes closed
Week 4	10 minutes eyes closed	13 minutes RHI or relaxation	10 minutes eyes closed

questionnaires (\$25) and diary (\$25). Participants also will be given \$25 to pay for parking and gas, or for public transportation for the visit to the UW HSC. The 20 participants undergoing qEEG will receive an additional \$50 after completing each qEEG for a total of \$150. They also will be given \$25 to pay for parking and gas, or for public transportation to the UW IBIC for two visits (\$50). Data will be managed using REDCap (Research Electronic Data Capture).⁹ The RA will be responsible for data entry and I will verify its accuracy.

Data Analysis. *Aim 1: Does the RHI work? Evaluate the efficacy of RHI in reducing self-reported pain intensity (primary outcome) and pain interference, anxiety, depression, fatigue, and sleep disturbance (secondary outcomes) at 4 weeks compared to the attention control condition (relaxation recording).* We will use ANCOVA controlling for baseline scores and co-variates including pharmacologic treatments to test whether *mean pain intensity* at week 4 differs between the RHI and relaxation groups. The same analysis will be done for the secondary outcomes. In addition, we will graphically describe trajectories of daily pain and anxiety at Weeks 0, 2, and 4, based on the Daily Diary for pain intensity and anxiety in the RHI and relaxation groups. This approach will allow us to understand whether an increased dose of the intervention (i.e., 4 weeks vs. 2) is necessary to achieve significant reduction in pain intensity.

Aim 2: For whom does the RHI work? Examine if psychological factors (hypnotic suggestibility, mental absorption, treatment outcome expectancy) moderate the relationship between RHI and pain intensity at weeks 0, 2, and 4. The following multiple regression model will be estimated:

$\text{PAIN}_{\text{week}2} = \text{Pain}_{\text{week}0} + \text{PSY}_{\text{week}0} + \text{RHI} + \text{PSY}_{\text{week}0} \times \text{RHI}$, where moderator effects will be indicated by the interaction term $\text{PSY}_{\text{week}0} \times \text{RHI}$. We will measure Cohen's d for each of the levels of the moderator and compare them to determine the moderator effect. The resulting effect size will be used to estimate the sample size in a larger follow-up study (e.g., R01).

Aim 3: How does the RHI work? Compare brain states as measured by qEEG in cancer survivors with chronic pain receiving the RHI relative to the attention control condition (relaxation recording) at weeks 0, 2, and 4. We will use multiple regression models controlling for baseline scores and co-variates (e.g., medication use) to compare the change in theta activity from *pre-session* to *during session* between RHI and relaxation groups. We will also compare the change in theta activity from *pre-session* to *post-session* between groups. This will be replicated for all 3 time points: Weeks 0, 2, and 4. Replication allows us to assess if theta activity

changes during the study period. We will also explore other bandwidths (e.g., alpha, beta, delta, gamma) in our analysis. Medium or larger effect sizes for changes in bandwidth activity will be used to indicate that more formal testing in future research is warranted. *Explore the mediation effects of brain states (theta activity) on pain intensity at weeks 0, 2, and 4.* Cross-sectional analyses will examine mediation at weeks 0, 2, and 4 for how RHI and theta activity jointly affect pain intensity. The mediating effects model implicit in **Figure 1** will be tested using multiple regression models. Effect sizes (Cohen's d) will be computed for looking at the biological mechanism in a larger, more definitive study. *Structured interviews.* Transcribed interview data will be organized in ATLAS.ti7 (Scientific Software Development, Berlin, Germany). Content analysis^{10,11} will be used to understand the barriers and facilitators associated with undergoing qEEG measurement and perceptions on how the intervention works to reduce pain.

In summary, this study is extremely important because it will provide scientific evidence on the efficacy of a symptom self-management intervention that cancer survivors can easily use to manage a distressing symptom. Furthermore, this study is innovative in that it will increase our understanding of how this intervention works and who will most likely experience pain reduction when using this low-cost, accessible, and convenient intervention.

References

1. Morgan AH & Hilgard JR. (1978). The Stanford Hypnotic Clinical Scale for adults. *The American Journal of Clinical Hypnosis*, 21, 134-47.
2. [name] M. (2011). *Hypnosis for chronic pain management: therapist guide*. Oxford University Press.

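### Expectancy is rated after the arm is disclosed and the recording taught, so its Aim 2 interaction should not be read as baseline moderation

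*Combined protocol and SAP*

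**What the plan says.** Under Data Collection Schedule and Procedures, the Week 0 Study Visit is a numbered sequence in the combined protocol and SAP: "3) share group assignment; (4) provide teaching about the RHI or relaxation recording, and participant study responsibilities; (5) administer the Credibility/Expectancy Questionnaire".

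Group Assignment agrees. Once the participant has returned the baseline questionnaires and "completes the in-person hypnotic clinical measure at the Week 0 study visit, the appropriate envelope will be opened". Expectancy is not among the things that must come first. It also cannot be among the mailed forms ("Baseline questionnaires and consent form will be mailed to the participant with instructions to complete 1-2 days before the Week 0 study visit"), because those are collected at step 1 and the expectancy form is given separately at step 5. Table 2b lists the "Credibility/Expectancy Questionnaire 4-item questionnaire, test-retest 0.62-0.78" and marks it at Week 0 only.

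Under Data Analysis, Aim 2 asks which patients benefit and plans to "Examine if psychological factors (hypnotic suggestibility, mental absorption, treatment outcome expectancy) moderate the relationship between RHI and pain intensity". All three factors enter the same regression as a Week 0 score, "where moderator effects will be indicated by the interaction term". The plan adds: "We will measure Cohen's d for each of the levels of the moderator and compare them to determine the moderator effect". Then: "The resulting effect size will be used to estimate the sample size in a larger follow-up study (e.g., R01").

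**The concern.** A moderator analysis asks whether the treatment effect differs between kinds of patient. Randomization supports that comparison only if the characteristic is fixed before allocation, because then people with the same value in the two arms are comparable. Suggestibility meets this condition. Expectancy does not, because the arm and the teaching can change the score and the two arms rate different recordings. Being labelled Week 0 does not make it a pre-assignment measure.

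At stake is one of the three Aim 2 conclusions. A non-zero interaction could arise without any true moderation, and a zero could hide some. The effect size would then carry the problem into the design of the next study. Rating expectancy after teaching is a sensible credibility check. The problem is only its use as a baseline moderator.

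**Working it through.** **1. Timing set side by side**

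| Aim 2 factor | When measured | Before disclosure? |
|---|---|---|
| Hypnotic suggestibility | Step 2, before the envelope is opened | Yes |
| Absorption | Week 0; apparently among the mailed forms (inferred, not stated separately) | Apparently yes |
| Expectancy | Step 5, after disclosure (3) and teaching (4) | No |

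**2. The plan's own figure.** Table 1 is the only power figure. SD × √(2/50) × (1.960 + 0.842) gives 0.56, 0.84 and 1.12 for SD 1.0, 1.5 and 2.0. The noncentral t gives 0.566, 0.849 and 1.132, against the stated 0.57, 0.85 and 1.13. The table reproduces, but it concerns the main effect of arm. The plan gives no inputs for the interaction, so everything below is illustration.

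**3. Assumptions.** The design is 50 per arm with the planned model: week-2 pain on week-0 pain, expectancy E, arm, and E × arm, with a two-sided 5% test. Pain is in SD units and the RHI effect is −0.50. The correlation of expectancy with week-2 pain is −c, with c = 0.5 or 0.3. Week-0 and week-2 pain correlate 0.5 (or 0.6 in some settings of (a) and (b)). Cohen's d is taken in each half of a median split of E. There were 6,000 to 8,000 simulated trials per setting.

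**4. Results**

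(a) *All RHI-arm ratings shift by 0.5 SD.* The slope on E stays −c in both arms, so the interaction is −c − (−c) = 0 (simulated 0.001, rejection 5.3%). The arm effect at a given score moves by c × 0.5: −0.50 + 0.25 = −0.25 (c = 0.5) or −0.50 + 0.15 = −0.35 (c = 0.3). Within-level d falls from 0.56 to 0.38, or from 0.53 to 0.43. The difference in d between levels stays within 0.005 of zero.

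(b) *RHI-arm ratings spread k times wider.* The interaction is c(1 − 1/k). Rejection is 5.5–6.7% at k = 1.1. At k = 1.25 it is 7.3–13.5% (c = 0.5) or 5.8–7.0% (c = 0.3). At an extreme k = 1.5 it is 12.2–32.9% or 6.4–11.9%. The difference in d again stays within 0.005 of zero.

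(c) *Each arm rates its own recording; pain depends on RHI expectancy equally in both arms, so there is no true moderation.* Let ρ be the correlation between a person's two expectancies. The RHI-arm slope is −c and the control slope is −cρ, so the planned interaction is −c(1 − ρ).

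| | ρ = 0.5 | ρ = 0.7 | ρ = 0.9 |
|---|---|---|---|
| Interaction, c = 0.5 | −0.25 | −0.15 | −0.05 |
| Rejection | 34% | 16% | 6% |
| Difference in d | 0.42 | 0.25 | 0.08 |
| Interaction, c = 0.3 | −0.15 | −0.09 | −0.03 |
| Rejection | 14% | 8% | 6% |
| Difference in d | 0.24 | 0.14 | 0.05 |

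Hand check of the first cell: the residual variances are 1 − 0.25 − 0.25 = 0.50 and 1 − 0.25 − 0.0625 = 0.6875, so SE ≈ √((0.50 + 0.6875)/50) = 0.154 and z ≈ 0.25/0.154 = 1.62. That implies about 37% rejection on a normal approximation, close to the simulated 34%. If ratings also correlate −0.3 with baseline pain, rejection is 21, 10 and 6% (c = 0.5) or 7, 6 and 5% (c = 0.3). If everyone rates the RHI, rejection is 5.1%.

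(d) *Pain follows expectancy for the recording received, so RHI expectancy truly moderates.* The planned interaction is −c − (−c) = 0 and rejects in 5%. A pre-allocation rating of the RHI by everyone would show −c(1 − ρ) and reject in 35, 16 and 6% (c = 0.5) or 14, 8 and 6% (c = 0.3).

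(e) *c = 0.* Rejection is 5.0%; there is no bias by these routes.

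**5. Separate simulation, other mechanisms.** Here the arm effect is −0.57 SD, the expectancy slope −0.2 to −0.5, the rating noise 0.6 SD (0.8 in the RHI arm in one setting), and there is no true moderation. A pre-disclosure rating rejects in 5.0%. A mean shift of 0.5–1 SD gives 4.6–5.5%. A 1.5-fold stretch gives 5.7–10.9%, lower than in (b) because rating noise dilutes it. If the RHI rating no longer reflects prior expectancy, rejection is 13–53%.

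**6. Scale.** With 25 per arm in each half, the SE of d is about √(2/25) = 0.28, and of the difference about 0.28 × √2 = 0.40. Simulated values are 0.29–0.30 and 0.41–0.43. The largest shift in (c), 0.42, is about one such SD.

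**The case against.** The order of steps is not in dispute, so the case against concerns weight.

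- Every magnitude input is assumed. Several plausible mechanisms leave the interaction at zero, and large inflation needs a strong expectancy–pain link with a low ρ or a much wider spread. This stands.
- Scenario (c) needs RHI expectancy to predict pain in controls who never receive the RHI. If general optimism drives that link, ρ should be high and rejection near 6%. This is fair, but the documents do not settle ρ.
- Expectancy could mean expectancy for the assigned treatment. The zero in (d) would then be a correct answer, to the question of whether expectancy tracks outcome differently by arm. That reading is possible, but it is not the question Aim 2 poses.
- The effect size carried forward may be the difference in d, in which case the within-level shifts in (a) do not matter. The wording allows either reading.
- Imprecision at 100 participants is at least as large a threat to sizing the next study. This is true, but noise does not turn a post-assignment score into a baseline one.
- The rating comes before scheduled use of the recordings. That removes the influence of experienced benefit, but not of disclosure and teaching.

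**Conclusion.** The concern holds and should be fixed. The sequence is explicit, nothing elsewhere in the document provides an earlier rating or a caveat, and the analysis treats the score as if it preceded allocation. The conclusion that the interaction is not a baseline-moderator contrast rests on the text alone and needs none of the assumed inputs.

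Bias is possible, not certain, and its size cannot be found from the documents. In the main illustration the planned test rejects between 5% and 34% of the time without true moderation, and the spurious difference in d runs from 0 to 0.42. It can equally show nothing when moderation exists. The planned data cannot tell these cases apart. The Aim 1 analysis is not affected, nor is suggestibility; the same goes for absorption if, as appears, it is among the mailed forms.

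**What to change.** **Minimum.** In Aim 2, remove expectancy as now timed from the list of baseline moderators. Report it by arm as a post-assignment exploratory variable and credibility check, and state that its effect size will not be used to plan the follow-up study. This costs only a text change.

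**If expectancy is to stay a moderator.** Between steps 2 and 3, after a brief neutral description, have every participant complete the same 4-item form about the RHI. Use that score as the Week 0 term and keep the post-teaching rating as the credibility check. Rating both recordings at that point is a reasonable variant. The cost is one short form, with no extra visit or staff.

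The option has drawbacks. A rating before teaching is more hypothetical. Controls rate a recording they will not receive and may be disappointed. A form given straight after the hypnotic scale may partly reflect performance on it, as the present timing may too. A pre-allocation rating cannot be recovered for participants already allocated.

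### The qEEG substudy is offered after the participant knows the arm, so the Aim 3 contrast is not fully protected by randomisation; the offer could be made before the envelope is opened.

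*Combined protocol and SAP*

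**What the plan says.** The Design paragraph sets the qEEG sample by score level and arm: "Five participants from each group who score low (score = 0 - 1") and "5 participants from each group who score high (score = 4 - 5"). The payment paragraph gives the total: "The 20 participants undergoing qEEG will receive an additional \$50 after completing each qEEG".

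Two sections fix the order of events.

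- **Group Assignment.** Once the participant "completes the in-person hypnotic clinical measure at the Week 0 study visit, the appropriate envelope will be opened" and the arm is disclosed. The next sentence reads: "Based on their high or low hypnotic suggestibility score, eligible participants will be invited to participate in the qEEG study arm".
- **Week 0 Study Visit.** The numbered list runs "2) administer the Stanford Hypnotic Clinical Scale; (3) share group assignment; (4) provide teaching about the RHI or relaxation recording", then the Credibility/Expectancy Questionnaire as item 5, and last "6) inform participant if they are eligible for the qEEG measurement".

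The Week 0 section also foresees refusals: it provides for people who are ineligible for qEEG "or eligible but not interested in participating".

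Under Data Analysis, Aim 3 compares theta change between the RHI and relaxation groups by regression, adjusting for baseline scores and covariates, with medication use as the example. It then explores theta as a mediator of pain intensity. Effect sizes of medium or larger are the signal for formal testing in later research.

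**The concern.** A participant deciding about qEEG has just been told and taught either hypnosis or relaxation. The assigned recording is played during the EEG session, so the two arms are deciding about different experiences. The research assistant who makes the offer has also just disclosed the arm. No rule says which eligible people fill the five places in each cell.

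Acceptance is a real choice: it means three EEG sessions and two further trips. If the people who accept after hearing hypnosis differ in motivation or expectancy from those who accept after hearing relaxation, part of any between-arm difference in theta reflects who accepted and not what they listened to. Taking 5 low and 5 high scorers per arm balances suggestibility level, but not motivation or expectancy. The mediation analysis carries the same problem, and the medium-effect rule would be applied to the mixture.

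Nothing in the documents records willingness before allocation, reports refusals by arm, or adjusts for selective acceptance.

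**Working it through.** **1. The plan's own count.** 5 participants × 2 score levels × 2 arms = 20, or 10 per arm. This agrees with the payment paragraph. Table 1 concerns the main trial and plays no part here; no power figure is given for Aim 3.

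**2. Order of events.** The two sections agree, so this is not a slip of wording.

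| Week 0 step | What becomes known |
|---|---|
| 2 | Suggestibility score, hence eligibility (0-1 or 4-5) |
| 3 | Arm |
| 4 | Content and use of the assigned recording |
| 5 | Expectancy rating |
| 6 | Eligibility for qEEG, with the option to decline |

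Eligibility and willingness could both be established at step 2. Only whether a place is still open depends on the arm.

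**3. Illustrative size.** All inputs are assumptions, because the documents give no acceptance rates. Let willingness W be standard normal, and let a fraction p of the arm accept, namely those with W above c, where P(W > c) = p. The mean of W among acceptors is φ(c)/p:

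- p = 0.9: 0.1755/0.9 = 0.195
- p = 0.8: 0.2800/0.8 = 0.350
- p = 0.6: 0.3863/0.6 = 0.644
- p = 0.5: 0.3989/0.5 = 0.798

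Let W have correlation r with the response, with no true treatment effect. Then bias (RHI minus relaxation) = r × (mean of W in RHI acceptors − mean of W in relaxation acceptors).

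| Accept, RHI vs relaxation | Difference in W | Bias, r = 0.3 | Bias, r = 0.5 |
|---|---|---|---|
| 80% vs 80% | 0 | 0 | 0 |
| 80% vs 60% | −0.294 | −0.09 SD | −0.15 SD |
| 80% vs 50% | −0.448 | −0.13 SD | −0.22 SD |
| 90% vs 50% | −0.603 | −0.18 SD | −0.30 SD |

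With r = 0 the bias is zero at any acceptance rates.

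**4. Direction.** The arm with the higher acceptance rate is the less selected and has the lower mean willingness. If that arm is RHI and r is positive, the bias runs against RHI, as in the table. Exchange the arms, or make r negative, and every sign reverses.

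**5. Comparison with noise.** With 10 per arm the standard error of d is about √(2/10) = 0.45. With no effect and no bias, |d| ≥ 0.5 corresponds to |t| ≥ 0.5/0.447 = 1.118 on 18 degrees of freedom, which has probability of about 28%. The difference detectable with 80% power is about d = 1.32. In simulation (20,000 trials, unadjusted t-test, nominal 5%) at r = 0.5, the false-positive rate was 8.3% for 80% vs 50% and 10.8% for 90% vs 50%. The plan sets no alpha for Aim 3, so these rates only indicate scale.

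**The case against.** Several counter-arguments have force.

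- **Participants are still randomised.** A reader might infer that Aim 3 has become a non-randomised comparison. The documents do not support that. Everyone in the substudy was randomised, and bias arises only if acceptance differs by arm and relates to response. Both arms are offered the same number of sessions, the same listening time and the same payment, which favours similar acceptance.
- **A false signal is not the likelier outcome.** A reader might infer that the bias could by itself reach a medium effect (d = 0.5, an assumed benchmark) and produce a false go-ahead. With 90% vs 40% acceptance and r = 0.7 the formula does give 0.54 SD (difference in W 0.771 × 0.7). But nothing in the documents supports inputs that extreme, and if RHI has the higher acceptance and r is positive, the bias would hide an RHI effect.
- **The quota depends on arm.** Places are counted per arm, so inviting after allocation has an operational reason. It justifies filling places after allocation, not asking about willingness then.
- **Adjustment is possible.** The covariate list for Aim 3 is open, and absorption and expectancy are measured at Week 0. Neither is named for Aim 3, however, and 20 participants leave little room for covariates.
- **qEEG may have been discussed earlier.** The letter, the telephone call and the consent form precede the envelope, and the consent pages are not available for review. The Week 0 section still places the eligibility notice and the chance to decline after disclosure.
- **The consequence is limited.** Aim 3 is exploratory, and its sampling error exceeds the plausible bias. This lowers the priority. It is no reason to keep a systematic error that can be avoided at almost no cost.

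**Conclusion.** The point stands as a cheap improvement to the design. The order of steps is explicit in two sections, the qualifying score is known before the arm is disclosed, and refusals are foreseen, so the Aim 3 contrast and its mediation analysis are not fully protected by randomisation.

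The size cannot be determined from the documents. The 0.09 to 0.30 SD rests wholly on the assumed 20 to 40 point gaps in acceptance, correlations of 0.3 to 0.5 and a single normal willingness trait. The direction is unknown. The primary comparison in Aim 1 does not depend on who enters the substudy and is unaffected.

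**What to change.** Amend Group Assignment and the Week 0 Study Visit as follows.

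1. After the suggestibility scale is scored and before the envelope is opened, ask every participant scoring 0-1 or 4-5 whether they agree to qEEG, and record yes or no.
2. After allocation, fill each arm-by-score cell of 5 in order of enrolment from those who agreed. Do not approach again anyone who declined.
3. Report withdrawals after disclosure by arm and score level. People can still change their minds once they know the arm, so the change reduces the problem and makes the remainder visible, but does not abolish it.

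**Cost.** One step moves within the same visit, with the same staff. The qEEG sample stays at 20 and Table 1 does not change. Some who agree will find their cell full and must be told beforehand that this is possible. The invitation would also come before the expectancy questionnaire, so it should be worded without saying whether the score was high or low.
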